7.6. Early Termination Visit (if needed)

The following activities will be performed at the early termination visit for subjects who withdraw, or are withdrawn or terminated from this study:

- Obtain interim medical history, including an assessment for new medical conditions by interview of subjects and review of medical charts, if applicable, and note any changes since the previous clinic visit or phone call.

- Obtain vital signs: heart rate, blood pressure, and temperature. Subjects will be asked not to eat or drink anything hot or cold, or smoke within 10 minutes prior to taking an oral temperature.
- Study personnel will collect infant length, weight, and head circumference as well as birth outcomes on the appropriate data collection form.
- Review solicited AEs (if within 8 days after the study vaccination or if after the 8-day period but the AE information had not previously been collected).
- All concomitant medications/vaccinations will be recorded on the appropriate data collection form (if within the period of collection of concomitant medications).
- Review adverse events (if within the collection period for AEs).
- Review serious adverse events, if within the collection period for SAEs.
- A targeted physical examination may be performed on the mother and/or infant by a study clinician licensed to make medical diagnoses and listed on the Form FDA 1572 as the site principal investigator or sub-investigator, if indicated based on review of interim medical history.
- Examine study vaccination site (if within 30 days after the study vaccination).
- Record birth outcomes, if applicable.

7.7. Unscheduled Visit (if needed)

Unscheduled visits may occur at any time during this study. Any of the following activities may be performed:

- Obtain interim medical history, including an assessment for new medical conditions by interview of subjects and review of medical charts, if applicable, and note any changes since the previous clinic visit or phone call.
- Obtain vital signs: heart rate, blood pressure, and temperature. Subjects will be asked not to eat or drink anything hot or cold, or smoke within 10 minutes prior to taking an oral temperature.
- Study personnel will collect infant length, weight, and head circumference as well as birth outcomes on the appropriate data collection form.
- Review solicited AEs (if within 8 days after the study vaccination or if after the 8-day period but the AEs had not previously been collected).
- Review concomitant medications/vaccinations (if within the collection period for concomitant medications).

- Review adverse events (if within the collection period for AEs).
- Review serious adverse events, if within the collection period for SAEs.
- A targeted physical examination may be performed on the mother and/or infant by a study clinician licensed to make medical diagnoses and listed on the Form FDA 1572 as the site principal investigator or sub-investigator, if indicated based on review of interim medical history.
- Examine study vaccination site (if within 30 days after the study vaccination).
- Record birth outcomes, if relevant.

8. STUDY PROCEDURES/EVALUATIONS

8.1. Clinical Evaluations

Complete medical history to determine eligibility will be obtained by review of the medical record supplemented by interview for pregnant women. The information will be obtained at the screening visit and will be updated on Day 1, prior to study vaccination. Subjects and records, when available, will be queried regarding a history of significant medical disorders of the head, eyes, ears, nose, throat, mouth, cardiovascular system, lungs, gastrointestinal tract, liver, pancreas, kidney, urologic system, nervous system, blood, lymph nodes, endocrine system, musculoskeletal system, skin, and genital/reproductive tract. A history of any allergies, cancer, immunodeficiency, psychiatric illness, substance abuse, and autoimmune disease will be solicited. At follow-up visits, an interim medical history will be obtained by interview of the subjects and review of the medical chart of pregnant women when needed, noting any changes since the previous clinic visit or phone call. The interim medical history will include an assessment for new medical conditions and symptoms.

Medications history (concomitant medications) will include a review of all current medications through the intervals described in [Section 6.6](#) (Concomitant Medications/Treatments).

Prescription and over-the-counter drugs will be included as well as vaccines, herbals, vitamins, and supplements. Use of any new medication should prompt evaluation for the presence of a new diagnosis, unless the medication is an expected medication in the care of a pregnant woman. Examples of medications used in the care of pregnant women that would not prompt evaluation for a new diagnosis would be prenatal vitamins for all women and RhoGAM for Rh(D)-negative women. Assessment of eligibility will include a review of all permitted and prohibited medications per the Subject Inclusion and Exclusion Criteria. In addition, the site principal investigator or appropriate sub-investigator may identify other medications that should not be used due to a risk to subject safety or assessment of reactogenicity and immunogenicity.

At the screening visit, a targeted physical examination, if indicated based on subject's complete medical history, may be performed by a study clinician licensed to make medical diagnoses and listed on the Form FDA 1572 as the site principal investigator or sub-investigator. For pregnant women, information from a physical exam performed by the subject's clinician may also be used. On Day 1, prior to the vaccination, and as needed at follow-up visits after vaccination, a targeted physical examination may be performed by a study clinician licensed to make medical diagnoses and listed on the Form FDA 1572 as the site principal investigator or sub-investigator, if indicated based on the subject's interim medical history. Targeted physical examinations are performed to investigate further symptoms reported by the subject that may have relevance to the study.

Vital signs (oral temperature, pulse, and blood pressure) will be collected on Day 1 prior to the administration of the study treatment and on subsequent visits as denoted in the study schedule.

Vital signs assessed on Day 1 prior to study vaccination will be considered as baseline. Subjects will be asked to not eat or drink anything hot or cold, or smoke within the 10 minutes prior to taking an oral temperature.

Solicited event assessments will include an assessment of solicited adverse events occurring from the time of vaccination (Day 1) through Day 8. These assessments include injection site (local) reactions of ecchymosis (bruising), erythema (redness), induration (hardness)/edema (swelling), pain, and tenderness as well as systemic reactions including fever, feverishness (chills/shivering/sweating), fatigue (tiredness), malaise (general unwell feeling), myalgia (body aches/muscular pain exclusive of the injection site), arthralgia (joint pain exclusive of the injection site), headache, nausea, and allergic reaction (pruritus/urticaria). Pre-administration solicited systemic event assessments will be performed prior to study vaccination to establish baseline, then the study vaccination will be given.

Subjects will be observed in the clinic for at least 30 minutes after the study vaccination. The study vaccination site will be examined, post-administration solicited event assessments will be performed, and any AE/SAEs will be assessed and recorded on the appropriate data collection form prior to discharge from the clinic. A field worker will visit all subjects on Days 4 and 8 to collect information on solicited adverse events and any AE/SAEs. The study vaccination site will also be examined on Day 31.

8.2. Laboratory Evaluations

8.2.1. Clinical Laboratory Evaluations

Clinical screening laboratory parameters are not included in the routine evaluation for eligibility. If the medical record or history reveals laboratory abnormalities that might preclude eligibility or affect subject safety or the investigator's ability to assess the safety, tolerability, or immunogenicity of the vaccine, the investigator may use that information to determine eligibility.

8.2.2. Special Assays or Procedures

Immunogenicity

Laboratory assays to determine serum antibody concentrations to Tdap antigens will be performed at VTEU site laboratories using qualified ELISAs. Cytokines produced by peripheral blood cells from vaccinated mothers and infants stimulated with DTwP antigens will be measured using commercial and validated multiplex technology. Subjects who withdraw early will have assays run on available samples.

Breast Milk and Colostrum: The exploratory measurement of antibody to Tdap antigens in colostrum/breast milk will be performed at VTEU site laboratories using qualified ELISAs. These assays have not been validated for colostrum/ breast milk.

Laboratory personnel performing all assays will be blinded as to the allocation arm of pregnant subjects (Tdap vs. Td), study visit number, and whether the samples are from adult or infant subjects. The volume of venous blood and colostrum/breast milk to be collected for assays is presented in [Table 2](#).

Table 2: Specimen Volumes (mL) for Pregnant Women and Infants

Study Visit Number	V00	V01	V02	V03	V04	V05	V06	V07	V08	Total
Study Day (pregnant women)	Screen	D1	D4±1d	D8+3d	D31±4d	Birth+3d	Birth+D42±5d 6 weeks post partum	Birth+D70±5d or D130±5d 10 or 18 weeks post partum*	Birth+D180±7d 6 months post partum	
Study Day in relation to delivery	pre	pre	pre	pre	pre	1	42	70-130	180	
Study vaccination		X								
Pregnant women blood		30 ^{&}	--	--	30	30	--	--	30	120 mL
Umbilical cord blood			--	--		20-30	--		--	20-30 mL
Infant blood			--	--		5 [#]	5%	5%	5	15 mL (20 mL, max) [#]
Colostrum or breast milk			---	--		10-20	10-20	10-20	10-20	40-80 mL

#2-5 mL of infant blood will be taken by phlebotomy during the delivery admission only if cord blood cannot be obtained.

*One-half of woman-infant pairs will be randomized to the 10 week time point and one-half to the 18 week.

[&]Prior to receipt of tetanus-containing vaccine.

[#]Prior to receipt of DTwP.

8.2.3. Specimen Preparation, Handling, and Shipping

8.2.3.1. Instructions for Specimen Preparation, Handling, and Storage

Instructions for specimen preparation, handling, and storage are included in the protocol-specific MOP, as appropriate.

8.2.3.2. Specimen Shipment

Specimen shipment will occur at intervals during the course of this trial following all applicable International Air Transport Association (IATA) requirements and according to the specifics for storage temperature and documentation as detailed in the protocol-specific MOP, as appropriate. Further instructions for specimen shipment will be included in the protocol-specific MOP, as appropriate.

9. ASSESSMENT OF SAFETY

9.1. Specification of Safety Parameters

Safety will be assessed by the frequency and severity of the following:

- 1) Study vaccine-related Serious Adverse Events occurring from the time of the study vaccination through the visit 6 months postpartum (180 days of life for the infant visit) for pregnant subjects and infants. All SAEs during this timeframe will be assessed and documented.
- 2) Adverse Events related to pregnancy and the infant as delineated below in [Section 9.2.4](#). For the pregnant woman/mother: pregnancy loss, vaginal bleeding (antepartum or postpartum), post-abortal endometritis/salpingitis, preterm rupture of membranes, preterm contractions/labor/delivery, poor fetal growth, hypertension/pre-eclampsia/eclampsia, chorioamnionitis, postpartum endometritis, gestational diabetes mellitus. For the infant: preterm birth, low birth weight, neonatal complications, and congenital anomalies.
- 3) Solicited Adverse Events – reactogenicity events occurring from the time of study vaccination through 7 days after study vaccination (Day 8) or until resolution.
 - a. Injection site reactions including ecchymosis (bruising), erythema (redness), induration (hardness)/edema(swelling), pain, and tenderness.
 - b. Systemic reactions including fever (days 4 and 8 only during home visits), feverishness (chills/shivering/sweating), fatigue (tiredness), malaise (general unwell feeling), myalgia (body aches/muscular pain exclusive of the injection site), arthralgia (joint pain exclusive of the injection site), headache, nausea, and allergic reaction (pruritus/urticaria).
- 4) Unsolicited Non-Serious Adverse Events – all non-serious unsolicited adverse events will be assessed and documented, and all study vaccine-related non-serious adverse events occurring from the time of study vaccination through approximately 30 days after study vaccination (the Day 31 visit). For pregnant women who deliver before Day 31, unsolicited adverse events will be recorded until delivery.
- 5) Major Congenital Anomalies
Congenital Anomalies: In this study, we will report as SAEs all major congenital anomalies known prior to a mother/infant dyad completing the study. These outcomes must occur following maternal vaccination during gestation or the perinatal period (within the first 5 days after delivery) but the diagnosis may be confirmed anytime during participation. We define “major congenital anomaly” as “defects that are present at birth and that have surgical, medical, or serious cosmetic significance.” [33]

The following list of problems are among the conditions reported in the US National Birth Defects registry and would be deemed as examples of major congenital anomalies:

anencephaly, spina bifida, encephalocele, anophthalmia, microphthalmia, cyanotic congenital heart diseases, cleft lip or palate, tracheoesophageal fistula, rectal stenosis, major limb deformities including shortening, gastroschisis, omphalocele, and diaphragmatic hernia. Some problems that are congenital anomalies but would be considered minor include most simple birthmarks, single transverse palmar creases, clinodactyly, umbilical hernias, post-axial polydactyly, ankyloglossia, and epicanthal folds.

Positional deformations, such as molding or overriding cranial sutures, metatarsus adductus, tibial torsion, and genu varum are not to be recorded as major congenital anomalies. Normal variants, such as minor anomalies of the pinna, supernumerary nipples, and penile torsion are also not major congenital anomalies. If major congenital anomalies are found prenatally, before enrollment, women will be excluded from participation. Many minor congenital anomalies will typically only be noted at or soon after birth.

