9.6.2. Data and Safety Monitoring Board (DSMB)

Safety oversight will be conducted by a DSMB that is an independent group of experts that monitors subject safety and advises DMID. The DSMB members will be separate and independent of study personnel participating in this trial and should not have scientific, financial, or other conflicts of interest related to this trial. The DSMB will consist of members with appropriate expertise to contribute to the interpretation of the data from this trial.

The DSMB will operate under the rules of a DMID-approved charter that will be written at the organizational meeting of the DSMB. Procedures for DSMB reviews/meetings will be defined in the charter. Reports may include enrollment and demographic information, medical history, concomitant medications, physical assessments, clinical laboratory values, dosing compliance,

and solicited and unsolicited AE/SAEs. The DSMB will review SAEs on a regular basis and ad hoc during this trial. The DMID Medical Monitor and the ISM (as deemed necessary per [Section 9.6.1](#)) will be responsible for reviewing SAEs in real time.

Additional data may be requested by the DSMB, and interim statistical reports may be generated as deemed necessary and appropriate by DMID. The DSMB may receive data in aggregate and presented by treatment arm (pregnant women, infants). The DSMB may also be provided with expected and observed rates of the solicited AEs in an unblinded fashion and may request the treatment assignment be unblinded for an individual subject if required for safety assessment.

The DSMB will review grouped and unblinded data in the closed session only. As an outcome of each review/meeting, the DSMB will make a recommendation as to the advisability of proceeding with study vaccinations (as applicable), and to continue, modify, or terminate this trial.

The DSMB will conduct the following reviews:

- When safety data collected through Day 8 is available for 25% of pregnant study subjects.
- Ad hoc when a halting rule is met or DMID/DSMB chair may convene an ad hoc meeting if there are immediate concerns regarding observations during this trial.
- Final review meeting: 6 to 8 months after clinical database lock to review the cumulative unblinded data for this trial. The data will be provided in a standard summary format. The DSMB may be asked to provide recommendations in response to questions posed by DMID.

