11.4.2. Safety Data

Maternal safety and tolerability, and fetal/infant outcomes will be summarized for the Safety Analysis Population.

Solicited AEs will be summarized by severity on days 4 and 8 after the study vaccination and as the maximum severity over the 8 days. Additionally, solicited AEs will be analyzed by taking the most severe response over the follow-up period, dichotomizing into a binary variable (none versus mild, moderate, or severe) and using standard techniques, such as exact confidence intervals, to summarize the proportion of subjects reporting each symptom, any injection site symptom, and any systemic symptom.

Unsolicited AEs will be coded by Medical Dictionary for Regulatory Activities (MedDRA®) for preferred term and system organ class (SOC). The number of SAEs is expected to be small in this trial, so these events will be reported by detailed listings showing the event description, MedDRA® preferred term and SOC, date of study vaccination, event date, severity, relatedness, and outcome for each event. Non-serious unsolicited AEs will be summarized as number and percentage of subjects reporting at least one event in each MedDRA® preferred term and SOC, tabulated by severity and relationship to study product. Additionally, the proportion of subjects and exact 95% confidence intervals of AEs in aggregate and by MedDRA® categories will be computed.

The proportion of subjects reporting solicited or unsolicited AEs may be compared between treatment arms using Fisher's exact test. The number of untoward fetal outcomes, perinatal complications, and major congenital abnormalities is expected to be small and so these events will be reported by a detailed listing including the event description, MedDRA® preferred term and SOC, relevant dates (study vaccination and AEs), severity, relatedness, and outcome for each event. If more than 5% of pregnant women experience untoward fetal outcomes, perinatal complications, or infants born with major congenital abnormalities, the proportion of subjects with such events will be compared between the BOOSTRIX and Td treatment arms using Fisher's Exact test.

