### 9.3.1. Solicited Events and Symptoms

Systemic solicited adverse events will be collected in maternal subjects pre-vaccination, and systemic and local solicited adverse events will be collected 30 minutes post-vaccination and then daily for 7 days after vaccination and graded on a scale of 0 (absent), 1 (mild), 2 (moderate) and 3 (severe). Systemic events include fatigue, headache, nausea, allergic reaction, myalgia, malaise, arthralgia, feverishness and fever. Local events include pain at injection site, tenderness, ecchymosis, erythema, induration, and measurements of ecchymosis, erythema, and induration ([Table 8](#)).

The proportion of subjects reporting at least one solicited adverse event will be summarized for each solicited adverse event, any systemic symptom, any local symptom, and any symptoms. The 95% CI calculated using Clopper-Pearson methodology from a binomial distribution (SAS Proc Freq with a binomial (exact) option) will be presented and a Fisher's exact test will be performed to test for the difference in the proportion of subjects reporting a solicited adverse event ([Table 49](#) and [Table 50](#)).

For each systemic and local event, any systemic event, any local event, and any solicited event, the maximum severity over 7 days after vaccination will be summarized for the Safety population. The number and percentage of subjects reporting each event will be summarized by the maximum severity and treatment group ([Table 51](#)).

The number of subjects reporting a solicited adverse event will be summarized for each day post vaccination by treatment group in a summary table ([Table 52](#), [Table 53](#), and [Table 54](#)) and graphically in a bar chart ([Figure 225](#) and [Figure 226](#)).

Solicited adverse events by subject will be presented in [Listing 10](#) and [Listing 11](#).

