**16.2.7 Adverse Events****Listing 10: 16.2.7.1: Solicited Events – Systemic Symptoms**

Treatment Group	Subject ID	Post Dose Day	Assessment a	Symptom	Severity	Attributed to Alternate Etiology? b	Alternate Etiology
			MA				
			Clinic				

a MA = Data reported by subject on the Memory Aid and reviewed by clinic staff and reported in Solicited Events eCRF.  
b Grade 3 events only.  
Note: Clinic = Data collected by clinic staff during physical exam or symptom assessment (treatment administration record, in-clinic assessment, etc.)

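### Measured fever is limited to the Day 4 and Day 8 visits but summarized as fever over the whole week, and the SAP assumes daily readings that the protocol does not provide

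*Protocol*

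**What the plan says.** **Collection.** Protocol 9.1, item 3b, reads "Systemic reactions including fever (days 4 and 8 only during home visits"). SAP 4.5.1 repeats it. No other solicited reaction carries such a limit. Fever is graded on oral temperature from 38.0°C (Protocol Table 6). The visit windows are Day 4 (±1) and Day 8 (+3), so Days 3-5 and Days 8-11. The scheduled Day 1 temperature is taken before vaccination (Protocol 7.3). Appendix A places routine post-dose solicited assessments only at V01, V02 and V03.

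**Reporting.** Protocol 11.4.2 has solicited events "summarized by severity on days 4 and 8 after the study vaccination and as the maximum severity over the 8 days", and also analyses them by "taking the most severe response over the follow-up period, dichotomizing into a binary variable (none versus mild, moderate, or severe"). In SAP 9.3.1, "the maximum severity over 7 days after vaccination will be summarized for the Safety population", alongside the proportion with at least one event and Fisher's exact test. Fever is an ordinary row in Tables 49, 50 and 51.

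**The conflicting text.** SAP 9.3.1 also states that "systemic and local solicited adverse events will be collected 30 minutes post-vaccination and then daily for 7 days after vaccination", and its list of systemic events includes fever. Table 52 has a Fever row with a column for each of Days 2 to 8. Listings 10 and 11 carry the note "MA = Data reported by subject on the Memory Aid". The protocol provides for no memory aid, diary or home thermometer.

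**The concern.** Pain, headache or nausea since the last contact can be recalled at a visit. A temperature cannot. Two spot readings are a point prevalence at each visit, yet they are tabulated in the same form as recalled symptoms, as if they described the whole week. A fever that has come and gone by the time of a visit enters the table as no fever.

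Solicited systemic reactogenicity is part of the primary tolerability outcome, so this row will be read. Protocol 9.6.2 adds that "The DSMB may also be provided with expected and observed rates of the solicited AEs in an unblinded fashion". An observed rate from two readings set beside an expected rate from cumulative follow-up would look lower for reasons unrelated to the vaccine. One halting rule in Protocol 9.5 also counts Grade 3 quantitative systemic reactions within 7 days, and fever is the only reaction in the protocol's quantitative reactogenicity table.

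**Working it through.** **1. The plan's own figure.** The documents give no sample size or power for fever. The nearest figure is Protocol Table 9, the chance of seeing at least one event, 1 − (1 − p)^n. At p = 1%: 1 − 0.99^133 = 73.7% and 1 − 0.99^67 = 49.0%. Both match, as do the other rows.

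**2. Which fevers two visits can catch.** Let a fever start on Day k (k = 1 to 8) and last d days. It is caught if a visit day v satisfies k ≤ v < k + d.

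| Duration | Onset days caught, visits on Days 4 and 8 | Count |
|---|---|---|
| 1 day | 4, 8 | 2 of 8 |
| 2 days | 3, 4, 7, 8 | 4 of 8 |
| 3 days | 2, 3, 4, 6, 7, 8 | 6 of 8 |

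Moving V02 to Day 3 or Day 5 leaves the counts unchanged but changes which days are covered. With V02 on Day 3, a 2-day fever starting on Day 2 is caught. Moving V03 to Day 11, which the window allows, lowers the counts to 1, 2 and 3 of 8, and that reading lies outside the reporting week. These are counts of onset days. They become detection rates only if onset is spread evenly, which the documents do not say.

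**3. Effect of partial visibility.** Let s be the share of week-long fevers present at a reading. This is an assumption, shown from 1 to 0.25. The observed rate is s × p, and the Table 9 formula for a true 1% event becomes 1 − (1 − 0.01s)^n.

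| s | N = 133 | N = 67 |
|---|---|---|
| 1 | 73.7% | 49.0% |
| 0.75 | 63.3% | 39.6% |
| 0.5 | 48.7% | 28.5% |
| 0.25 | 28.3% | 15.4% |

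**4. Between-arm comparison.** With equal s in both arms, the difference s·p1 − s·p2 = s(p1 − p2) shrinks by s, and the ratio s·p1 / s·p2 = p1/p2 does not change. Illustration with assumed true rates of 10% and 2%: the difference falls from 8 points to 6, 4 and 2 at s = 0.75, 0.5 and 0.25, and the ratio stays at 5. Approximate power (normal approximation, two-sided 0.05, 133 against 67) falls from 54.5% to 40.0%, 25.0% and 11.4%.

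**5. Halting rule.** At n = 200 the threshold is max(5, 0.05 × 200) = 10 women. With an assumed true rate of vaccine-related Grade 3 fever of 10%, P(X ≥ 10) for X ~ Binomial(200, 0.10s) is 99.6%, 93.7%, 54.5% and 3.0% at s = 1, 0.75, 0.5 and 0.25. This is one look at full enrollment, to show direction only.

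**The case against.** The strongest objection is that the SAP plans daily data. SAP 9.3.1 says so with fever in the list, Table 52 has the columns, and the listings name the instrument. If women do record a daily temperature, the bias disappears and relabelling would discard valid data. This stands as a reason to settle the conflict first. It does not rescue the plan as written: SAP 4.5.1 contradicts SAP 9.3.1 within the same document, and the protocol gives no means of obtaining daily temperatures.

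A reader might infer that fever in the first two days cannot be seen at all. The documents do not support that. V02 may fall on Day 3, longer fevers persist to a visit, unscheduled visits may record temperature (Protocol 7.7), and women are told to report severe reactions.

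A reader might also want a percentage for the understatement. None is available, because no document gives onset, duration or visit-day distributions. Under assumed timings, a 24-hour fever starting in the first day is almost never caught, whereas 72-hour fevers are caught about 65% to 90% of the time. Any single range reflects the durations chosen.

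Nor is a between-arm difference lost. Both arms follow the same blinded schedule, so it is attenuated, with the ratio preserved under equal detection.

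The 5.5% fever rate in Protocol 2.3.1 is not a yardstick for the bias. It uses a threshold above 99.5°F and 14 days of monitoring, against 38.0°C (100.4°F) and one week here, and nothing says the DSMB's expected rate would come from it.

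Parts of the plan are already sound. Protocol 11.4.2 also reports Days 4 and 8 separately, Feverishness is solicited with its own row, and Table 51 already uses women with non-missing data as denominator.

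**Conclusion.** The point holds in a limited form. Two sets of passages disagree on how fever is collected. On the better-supported reading, the protocol's, the any-fever and maximum-severity results over 7 to 8 days rest on two readings and understate week-long fever. The direction assumes that some fevers resolve before or between visits and that unscheduled readings do not recover them all. A V03 reading on Days 9-11 could add a few fevers from outside the week, which works the other way. The size is not computable from the documents; the onset-day counts of 2, 4 and 6 of 8 show only how strongly it depends on duration. This is a question of reconciliation and labelling for one row of a primary tolerability outcome, and does not affect the recalled symptoms.

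**What to change.** 1. Reconcile Protocol 9.1 and SAP 4.5.1 with SAP 9.3.1, Table 52 (and Tables 53-54, which share its format) and Listings 10-11. State whether temperature is taken at the post-dose check on Day 1. If daily temperatures are collected, document the source in the protocol; the week-long summary can then stand.
2. If there is no daily source:
   - label the row in Tables 49-51 'Fever measured at the Day 4 or Day 8 visit';
   - use women with a temperature reading as denominator in Tables 49-50, in line with Table 51, in place of the total-population rule in SAP 9.3;
   - remove the other day columns for Fever from Table 52;
   - present Feverishness beside it as the week-long fever-type outcome, noting that it is subjective;
   - footnote in the DSMB and CSR tables that the figure is not a cumulative 8-day incidence and is not comparable with cumulative rates from other studies.
3. Align Protocol 11.4.2, so that Fever is reported by visit and left out of the summary described there "as the maximum severity over the 8 days".

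The cost is row labels, one denominator rule and a footnote. The report could no longer state an 8-day incidence of measured fever.
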